3.0 PATIENT SELECTION

3.1 Inclusion Criteria

1. AJCC 7th Edition stage 0 or I (*TisN0* \leq 2 cm or *T1N0*) histologically confirmed carcinoma of the breast, treated with partial mastectomy. Axillary sampling is required only for cases of invasive cancers. Tumor size is determined by the pathologist (*Section 6.2*). Clinical size may be used if the pathologic size is indeterminate. Patients with invasive cancer must have no positive axillary lymph nodes with at least 6 axillary lymph nodes sampled or a negative sentinel node.
2. Negative histologic margins of partial mastectomy or re-excision specimen. Margins generally are positive if there is invasive or noninvasive tumor at the inked resection margin, close but negative if the tumor is within 2 mm of the inked margin and negative if the tumor is at least 2 mm away from the inked edge.[41]
3. Invasive ductal, lobular, medullary, papillary, colloid (mucinous), tubular histologies, or mixed histologies (*lesions* \leq 2 cm) that are estrogen or progesterone receptor positive and do not exhibit HER2/neu gene amplification **OR** ductal carcinoma in situ (*lesions* \leq 2 cm).
4. Systemic therapy, if planned, must be adjuvant in nature and not be scheduled to begin for at least 4 weeks after completion of HG-PBI.
5. Good candidate for treatment per protocol in the judgment of the PI and/or treating physician following simulation.
6. Postmenopausal status.
7. Age \geq 50 years at diagnosis.
8. Able to understand and willing to sign IRB-approved written informed consent document.
9. English speaker.

3.2 Exclusion Criteria

1. Presence of distant metastases.
2. *In situ* lobular carcinoma or nonepithelial breast malignancies such as sarcoma or lymphoma.

3. Proven multicentric carcinoma (*tumors in different quadrants of the breast, or tumors separated by at least 4 cm*) with other clinically or radiographically suspicious areas in the ipsilateral breast unless confirmed to be negative for malignancy by biopsy.
4. Premenopausal status.
5. Histologically confirmed positive axillary nodes in the ipsilateral axilla. Palpable or radiographically suspicious contralateral axillary, supraclavicular, infraclavicular, or internal mammary nodes, unless there is histologic confirmation that these nodes are negative for tumor.
6. Prior non-hormonal therapy for the present breast cancer, including radiation therapy or chemotherapy.
7. Diagnosis of systemic lupus erythematosus, scleroderma, or dermatomyositis.
8. Diagnosis of a coexisting medical condition which limits life expectancy to < 2 years.
9. Diagnosis of psychiatric or addictive disorders that would preclude obtaining informed consent.
10. History of other malignancy \leq 5 years previous with the exception of basal cell or squamous cell carcinoma of the skin which were treated with local resection only or carcinoma *in situ* of the cervix.
11. Paget's disease of the nipple.
12. Skin involvement, regardless of tumor size.
13. Unsatisfactory breast for HG-PBI as determined by the treating physician. For example, if there is little breast tissue remaining between the skin and pectoralis muscle after surgery, treatment with HG-PBI is technically problematic.
14. Partial mastectomy so extensive that the cosmetic result is fair or poor prior to HG-PBI as determined by the treating physician.
15. Surgical margins which cannot be microscopically assessed or are positive at pathological evaluation.
16. Time between final definitive breast procedure to HG-PBI simulation is greater than 8 weeks.

3.3 Inclusion of Women and Minorities

Women and members of all races and ethnic groups are eligible for this trial. Because breast cancer occurs rarely in men, men will not be recruited for participation.

4.0 REGISTRATION PROCEDURES

Patients must not start any protocol intervention prior to registration through the Siteman Cancer Center.

The following steps must be taken before registering patients to this study:

1. Confirmation of patient eligibility
2. Registration of patient in the Siteman Cancer Center OnCore database
3. Assignment of unique patient number (UPN)

4.1 Confirmation of Patient Eligibility

Confirm patient eligibility by collecting the information listed below:

1. The registering MD's name
2. Patient's race, sex, and DOB
3. Three letters (or two letters and a dash) for the patient's initials
4. Copy of signed consent form
5. Completed eligibility checklist, signed and dated by a member of the study team
6. Copy of appropriate source documentation confirming patient eligibility

4.2 Patient Registration in the Siteman Cancer Center OnCore Database

All patients must be registered through the Siteman Cancer Center OnCore database.

4.3 Assignment of UPN

Each patient will be identified with a unique patient number (UPN) for this study. All data will be recorded with this identification number on the appropriate CRFs.

5.0 TREATMENT PLAN

5.1 Pre-Treatment Evaluations

These evaluations must take place no more than 28 days prior to initiation of treatment.

- History and physical exam by team radiation oncologist.
- Pre-implant cosmesis assessment by qualitative means and BRA (See Appendix III)
- Completion of the EORTC QLQ-30 and BR23 questionnaire

5.2 Radiation Therapy

5.2.1 Timing

HG-PBI must take place no more than 8 weeks from final definitive breast surgery.

5.2.2 Dose Specifications

PTV Cavity: total dose of 15-20 Gy in one fraction.

PTV Cavity + 1 cm Surface: minimum dose of 5-7 Gy in one fraction.

5.2.3 Technical Factors

The guidelines for IMRT in this trial will conform to the policies set by the Advanced Technology Consortium (ATC) and the National Cancer Institute (NCI), which may be found at: http://atc.wustl.edu/home/NCI/NCI_IMRT_Guidelines.html. Each of the target volumes and normal structures listed below must be delineated on each slice from the 3D planning CT in which that structure exists. Megavoltage photon beams with energies ≥ 6 MV and megavoltage electron beams are required. Proton beams are allowed. Co-60 teletherapy is allowed.

5.2.4 Localization, Simulation, and Immobilization

Simulation and treatment may be performed with the patient in the supine or prone position. Patients should be optimally positioned with alpha cradle casts or other methods of immobilization at the discretion of the treating physician.

Methods to minimize the cardiac exposure to RT like heart block, gating or breathhold are allowed at the discretion of the treating physician. For large-breasted patients, including those with a large inframammary skin fold, devices to improve positioning of the breast are permissible.

A treatment planning CT scan in the treatment position will be required to define the clinical target volumes (CTV) and planning target volumes (PTV). The CT required for generation of a virtual plan with 3DCRT or IMRT must be post-lumpectomy. Radio-opaque markers must be placed on external landmarks at the acquisition of the CT scan to facilitate contouring segmentation of the CT data-set. These markers should identify:

1. The lumpectomy incision
2. The outline of the palpable breast tissue circumferentially at least from 2 o'clock to 10 o'clock
3. The superior border of the breast tissue at 12 o'clock based on palpation

The CT should extend cephalad to start at or above the mandible and extend sufficiently caudally (or inferiorly) to the inframammary fold to encompass the entire lung volume. A CT scan image thickness of ≤ 0.5 cm should be employed. External skin localizing marks, which may include permanent tattoos, are allowed.

5.2.5 Treatment Planning/Target Volumes

The definitions for the CTV, PTV and normal structures used in this protocol generally conform to the 1993 ICRU report #50 titled Prescribing, Recording and Reporting Photon Beam Therapy and the RTOG-endorsed consensus guidelines for delineation of target and normal structures for breast cancer found at:

<http://www.rtog.org/CoreLab/ContouringAtlases/BreastCancerAtlas.aspx>.

5.2.5.1 Target Volumes and Normal Structures

Partial Mastectomy Volumes

PTV Cavity: Contour using all available clinical and radiographic information including the excision cavity volume, architectural distortion, lumpectomy scar, seroma and/or extent of surgical clips. Limit the PTV Cavity posteriorly at anterior surface of the pectoralis major and anterolaterally 5 mm from skin

and should not cross midline. In general, the pectoralis and/or serratus anterior muscles are excluded from the PTV Cavity.

PTV Cavity + 1 cm: PTV Cavity + 1 cm 3D expansion limited to exclude the part outside the ipsilateral breast and the first 5 mm of tissue under the skin (in order to remove most of the build up region for the DVH analysis) and excluding beyond the posterior extent of breast tissue (chest wall, pectoralis muscles and lung) when pertinent. The PTV Cavity + 1 cm should not cross midline. This PTV Cavity + 1 cm is the structure used for DVH constraints and analysis.

Breast Volumes

Breast CTV: Includes the palpable breast tissue demarcated with radio-opaque markers at CT simulation (see Section 5.2.3), the apparent CT glandular breast tissue visualized by CT, consensus definitions of anatomical borders, and the Lumpectomy CTV from the breast cancer atlas (see Partial Mastectomy Volumes above). The breast CTV is limited anteriorly within 5 mm from the skin and posteriorly to the anterior surface of the pectoralis, serratus anterior muscle excluding chest wall, boney thorax and lung. In general, the pectoralis and/or serratus anterior muscles are excluded from the breast CTV unless clinically warranted by the patient's pathology. The breast CTV should generally follow consensus guidelines found at:

<http://www.rtog.org/CoreLab/ContouringAtlases/BreastCancerAtlas.aspx>

Contralateral Breast

Includes the apparent CT glandular breast tissue visualized by CT and consensus definitions of anatomical borders from the RTOG Breast Atlas. In general the borders are:

Posterior border: At the anterior surface of the pectoralis, serratus anterior muscles excluding chest wall, ribs, boney thorax and lung/heart;

Medial border: The sternal-costal junction,

Lateral border: Varies based on the size of the breast but typically is at the mid-axillary line and excludes the ipsilateral latissimus dorsi muscle.

Cephalic border: Should be similar to that of the ipsilateral breast CTV

Caudal border: Inframammary fold and should be similar to that of the ipsilateral breast CTV.

Anterior border: Skin minus 5 mm to minimize inaccuracy of dose calculation at the skin surface.

Refer to breast contouring atlas found at:

<http://www.rtog.org/CoreLab/ContouringAtlases/BreastCancerAtlas.aspx>

Ipsilateral Lung

This may be contoured with auto-segmentation with manual verification.

Contralateral Lung

This may be contoured with auto-segmentation with manual verification

Heart

This is to be contoured on all cases, not just the left sided cases. The heart

should be contoured beginning just inferior to the level in which the pulmonary trunk branches into the left and right pulmonary arteries (PA). Above the PA, none of the heart's 4 chambers are present. The heart should be contoured on every contiguous slice thereafter to its inferior most extent near the diaphragm. The following structures, if identifiable, should be excluded from the heart contour: esophagus, great vessels (ascending and descending aorta, inferior vena cava). One need not include pericardial fat, if present. Contouring along the pericardium itself, when visible, is appropriate.

Thyroid

The thyroid is easily visible on a non-contrast CT due to its preferential absorption of iodine, rendering it "brighter" or denser than the surrounding neck soft tissues. The left and right lobes of the thyroid are somewhat triangular in shape and often do not converge anteriorly at mid-line. All "bright" thyroid tissue should be contoured.

5.2.5.2 Treatment Planning

CT-based planning with tissue inhomogeneity correction is required.

IMRT or 3D-CRT are permitted; arc based delivery is allowed; Co-60 teletherapy is allowed.

PTV Cavity should have a minimum dose of 15 Gy and maximum of 22 Gy. PTV Cavity + 1 cm should have a minimum dose of 5 Gy. With these goals a high dose gradient is achieved.

Normal tissue constraints: Skin structure is from skin to skin-3 in the region of the target $D_{max} \leq 22$ Gy, $V_{20} \leq 10\text{mL}$, $V_{10} \leq 15\text{mL}$, $V_3 \leq 20 \text{ mL}$. Contralateral Lung $D_{max} \leq 3$ Gy, $V_5 \leq 5\%$; Ipsilateral Lung $D_{max} \leq 7$ Gy, $V_5 \leq 5\%$; Heart $V_5 \leq 2\%$; Thyroid $V_5 \leq 10\%$.

5.3 General Concomitant Medication and Supportive Care Guidelines

Hormone therapy, chemotherapy, or biologic therapy is not allowed prior to HG-PBI, but may be started at least 4 weeks after the completion of HG-PBI.

5.4 Duration of Therapy

If at any time the constraints of this protocol are considered to be detrimental to the patient's health and/or the patient no longer wishes to continue protocol therapy, the protocol therapy should be discontinued and the reason(s) for discontinuation documented in the case report forms.

Treatment will consist of a partial mastectomy and single fraction of HG-PBI which will take place no more than 8 weeks after final definitive surgical procedure. Treatment will be discontinued if one of the following criteria applies:

- Documented and confirmed disease progression
- Death

- Adverse event(s) that, in the judgment of the investigator, may cause severe or permanent harm or which rule out continuation of study drug
- General or specific changes in the patient's condition render the patient unacceptable for further treatment in the judgment of the investigator
- Suspected pregnancy
- Serious noncompliance with the study protocol
- Lost to follow-up
- Patient withdraws consent
- Investigator removes the patient from study
- The Siteman Cancer Center decides to close the study

5.5 Duration of Follow-up

Patients will be followed according to the scheduled described in the study calendar for 5 years or until death, whichever occurs first. Patients removed from study for unacceptable adverse events will be followed until resolution or stabilization of the adverse event.

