2.0 OBJECTIVES

2.1 Primary Objectives

1. To quantify the tolerance of HG-PBI by estimating the rate of acute and late treatment-related grade 3 or higher toxicity (per CTCAE, v.4.0) or any other grade 4 or 5 toxicity attributed to the therapy. Toxicities of concern include breast pain, delayed wound healing, persistent seroma fluid accumulation, breast fibrosis and fat necrosis in the treated breast. Rare toxicities include radiation pneumonitis and pericarditis.
2. To estimate the ipsilateral breast tumor recurrence rate at 5 years after HG-PBI as the sole radiation therapy technique following partial mastectomy.

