Patients will be followed for 5 years. The primary goals of the study involve tolerance to treatment; the proportion of patients who are breast cancer free 5 years after treatment will be calculated with a 95% confidence interval. Cosmetic outcome will be assessed qualitatively by patients and physicians over the years after treatment. The two sets of scores will be plotted using histograms showing the proportion rating the outcome excellent, good, fair and poor. Kappa statistics with 95% confidence intervals will be calculated to assess the agreement between patient and physician scores before treatment, at 4-6 months at 1 year, and at subsequent visits. The pBRA will be used to assess cosmesis quantitatively. This instrument includes a formula expressing the extent of displacement of the treated breast relative to the contralateral breast and other anatomical features. pBRA scores will be plotted at the assessment points and presented graphically. Quality of life will be assessed using the 30 items of the EORTC QLQ-C30 and 23 items of the QLQ-B23 and the Visual Analog Scale for Pain. The QLQ-C30 includes 6 general questions and 24 questions in 9 subscales measuring physical, role, emotional, cognitive and social function, as well as global health status, nausea/ vomiting, pain and fatigue. The QLQ-B23 provides 23 questions in 8 breast cancer specific subscales, 4 measuring symptoms and 4 measuring function. Each of the subscales will be tabulated and presented graphically over the assessment times. Mixed repeated measures models will be generated to describe the nature of change in quality of life over time. Complications will be tabulated and frequencies presented graphically. The rate of mastectomy within five years of treatment will be calculated with a 95% confidence interval.

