11.6 Accrual

It is estimated that less than 10% of the patients treated in this study will be lost to follow up. Therefore, because the accrual goal is 50 evaluable patients (at 5 years post-treatment), target accrual is 55 patients to account for the 10% anticipated drop-out. It is estimated that patient accrual will take two to three years.

The investigators are well aware that several prior clinical trials that involved breast cancer at the Washington University Medical Center and the Siteman Cancer Center suffered from poor accrual. We believe that this trial will have excellent patient accrual. The primary source of patients who may be eligible for this study is via the breast surgeons of the Section of Endocrine and Oncologic Surgery here at Washington University. The chief breast surgeon is a collaborator in this study and is very supportive. The fact that a large fraction of patients with a common cancer disease are eligible for this study should lend further reassurance that this study ought to enjoy excellent patient accrual. The following series of conservative estimates provide an approximation of patient accrual: in 2012 more than four hundred patients with breast cancer were seen by physicians in the Department of Radiation Oncology. A conservative estimate is that 20% of these patients had an early stage breast cancer that would be eligible for this study. A further conservative estimate is that a third of these patients will consent to participate in this study. This yields an estimated accrual of just over 25 patients per year.

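### Section 5.5 follows patients removed for adverse events only until the event settles, which conflicts with the 5-year follow-up that the IBTR endpoint needs

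*Combined protocol and SAP*

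**What the plan says.** Section 5.5 has two sentences. The first covers everyone: "Patients will be followed according to the scheduled described in the study calendar for 5 years or until death, whichever occurs first". The second sets a different end for one group: "Patients removed from study for unacceptable adverse events will be followed until resolution or stabilization of the adverse event". It does not say whether calendar visits, or assessment for recurrence, continue for that group.

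Section 11.3 makes no exception: "Patients will be followed for 5 years". Section 11.6 sets the goal of 50 patients evaluable at 5 years and a target accrual of 55.

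Section 5.4 describes treatment as partial mastectomy and one fraction of HG-PBI, then gives a list introduced by "Treatment will be discontinued if one of the following criteria applies". One item is worded for a repeated drug: "Adverse event(s) that, in the judgment of the investigator, may cause severe or permanent harm or which rule out continuation of study drug". Another is "Investigator removes the patient from study", with no toxicity grade or other trigger attached.

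On attrition, Section 11.6 says "It is estimated that less than 10% of the patients treated in this study will be lost to follow up". The same section and the Schema also describe the 10% as drop-out.

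**The concern.** After a single fraction, an adverse event almost always arises when all treatment has been given. Removing the patient then stops nothing. Its only practical effect is on what is recorded afterwards, and the second sentence of Section 5.5 lets recording end when the event settles.

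Suppose a patient's event stabilizes at month 6 and she is removed. On the plain reading, the visits at 12, 18, 24 and 36 months and at years 4 and 5 are lost, which is 54 of 60 months. Her 5-year IBTR status, a primary endpoint, is then unknown. So is any later mastectomy, which Section 6.1 counts as a failure whatever the reason. Late complications, cosmesis and quality of life are lost too.

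The patients lost would be selected by toxicity, so their missing mastectomy, cosmesis and late-complication data could not be assumed to resemble the rest. The documents give no rule for how someone removed before 5 years enters the IBTR analysis, and no cut-off for fewer than 50 evaluable patients.

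**Working it through.** **Inputs.** Evaluable goal 50 and accrual 55 (Section 11.6); drop-out 10% (Schema, Section 11.6); expected grade 3-5 toxicity 5-8%, maximum 12% (Section 11.3); unacceptable IBTR 15.9%, assumed true IBTR 5.9%, alpha 0.05, and a favourable conclusion at 3 or fewer recurrences among 50 (Section 11.4). Sidedness of alpha is not stated.

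**1. The plan's own figures.** 50/0.9 = 55.6, which rounds up to 56; 55 × 0.9 = 49.5. The stated 55 is reproduced to within a patient. For the IBTR rule, take the error as the exact binomial chance of 3 or fewer recurrences when the true rate is 15.9%. P(X ≤ 3 | n = 50, p = 0.159) = 0.0324 and P(X ≤ 4) = 0.0835. So 3 is the largest cut-off that holds one-sided 0.05. Since 0.0324 exceeds 0.025, the rule reproduces only as a one-sided test. Power, P(X ≤ 3 | n = 50, p = 0.059), is 0.659, against the stated figure of about 70%.

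**2. How many patients the sentence could reach.** The lower bound is 0, because nothing requires removal. The upper bound assumes that every patient with grade 3-5 toxicity is removed: 55 × 0.05 = 2.75; 55 × 0.08 = 4.4; 55 × 0.12 = 6.6.

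**3. Evaluable patients at that upper bound.**

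| Toxicity | Removed | No other loss (55 − removed) | On top of 10% drop-out (49.5 − removed) |
|---|---|---|---|
| 5% | 2.75 | 52.25 | 46.75 |
| 8% | 4.4 | 50.6 | 45.1 |
| 12% | 6.6 | 48.4 | 42.9 |

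If removals are already inside the 10%, the figure stays at 49.5.

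**4. The IBTR rule at smaller n (exact binomial).**

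| Evaluable n | Error of ≤ 3 rule (p = 0.159) | Largest cut-off with error ≤ 0.05 | Power at that cut-off (p = 0.059) |
|---|---|---|---|
| 50 | 0.032 | 3 | 0.659 |
| 47 | 0.046 | 3 | 0.700 |
| 46 | 0.052 | 2 | 0.485 |
| 44 | 0.065 | 2 | 0.515 |

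The stated cut-off passes 0.05 at n = 46, that is, after 55 − 46 = 9 losses in total. Removal alone does not reach this even at 12% (48.4 remain). Removal on top of the full 10% drop-out does so at 8% and 12%, and stops just short at 5%.

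**5. A different handling.** Suppose removed patients instead stay in the denominator of 50 as recurrence-free. With 4 removed, the error is 0.052 if none of their recurrence risk was observed and 0.041 if half was. With 6 removed, it is 0.065 and 0.047. The result depends on a rule that the plan does not state.

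**6. The toxicity endpoint.** The objective is "estimating the rate of acute and late treatment-related grade 3 or higher toxicity", with no 5-year time point. Section 11.2 expresses it as a proportion of patients. A patient removed for a treatment-related grade 3 or higher event is already counted, and a second event cannot change her status. An event is missed only if a patient is removed for something that does not qualify and later has something that does.

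**The case against.** The best defence is that Section 5.5 can be read as a safety minimum: a removed patient is followed at least until her event settles. The Section 5.4 list stops treatment, not follow-up; no rule makes toxicity a ground for leaving the study; and 5 years is repeated in Sections 6.3, 7.0, 8.0 and 11.3. The clause may therefore apply to nobody. This stands as a limit on size. It does not remove the conflict, because the sentence does not say that it is a minimum, and site staff could reasonably stop visits once the event has stabilized.

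A reader might infer several stronger points that the documents do not support:

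- That both primary endpoints lose patients at 5 years, or that the primary toxicity rate is biased downward. Step 6 shows why this fails outside one narrow case.
- That patients harmed by the fraction leave the study. Only those whom the investigator chooses to remove could do so.
- That the observed IBTR is biased in a known direction. Nothing in the documents links toxicity to recurrence; what is shown is lost information and a shifted error rate.
- That the 10% allowance excludes removals. One sentence speaks of loss to follow-up, but the Schema and the rest of Section 11.6 say drop-out, which can include them.

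**Conclusion.** The conflict is real. On its plain reading, the second sentence of Section 5.5 gives removed patients less follow-up than the sentence before it and Section 11.3 promise, and less than Section 11.6 needs. In a single-fraction trial this shortening serves no treatment purpose.

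The size is uncertain and may be zero. The ceilings of 2.75 to 4.4 patients at expected toxicity, and 6.6 at the maximum, assume that every grade 3-5 patient is removed. The effect on the IBTR decision further assumes that removals come on top of the full 10% drop-out, that the test is one-sided, and that the cut-off stays at 3. Under those assumptions the error passes 0.05 at 46 evaluable patients; lowering the cut-off to 2 restores it but leaves power near 0.5. The damage to 5-year mastectomy, cosmesis, late-complication and quality-of-life data needs none of these assumptions beyond removal itself.

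**What to change.** Reconcile Section 5.5 with Sections 11.3 and 11.6 by replacing its second sentence. Suggested wording: *Every patient who receives HG-PBI remains on the Section 7.0 schedule for 5 years or until death, whatever adverse event occurs, unless she withdraws consent for follow-up. Adverse events unresolved at 5 years are followed to resolution or stabilization.*

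Add one line to Section 5.4 saying that its list governs delivery of treatment and not data collection. The criteria themselves need not change.

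In Section 11.3 or 11.4, state how a patient who still leaves before 5 years enters the IBTR analysis, and which cut-off applies if fewer than 50 are evaluable.

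The cost is a protocol amendment and continued visits for the few patients who would otherwise have been removed. Those visits are already on the study calendar, so no new procedure is added.
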